14.5.2. Co-Primary Safety Analyses

The primary safety analyses will be conducted on the safety population.

Grade 3 or Higher SLFs and Unacceptable Lens Fitting

Grade 3 of Higher SLFs (or Unacceptable lens fitting) will be analyzed using a Bayesian betabinomial model with correlated binary data¹⁴.

The Model:

Let Y (the percentage of eyes with grade 3 or higher SLFs [or unacceptable lens fitting]) be the sum of equicorrelated binary responses (Y_1 and Y_2 denotes left and right eyes, respectively) with probability of success p and correlation coefficient ρ .

The probability distribution of $Y = Y_1 + Y_2$ is obtained by the mixture of two variables. One of them follow a binomial distribution Bin(2, p) with probability of success p and mixing probability $(1 - \rho)$, and the other follows a modified Bernoulli distribution MBern(p), taking values 0 and 2, with probability of success p and mixing probability ρ :

$$P(Y = y | p, \rho) = (1 - \rho) Bin(2, p)I_{A1} + \rho MBern(p)I_{A2}$$

where $I_{A1} = \{0,1,2\}$, $I_{A2} = \{0,2\}$ and *p* is the probability of success (i.e. proportion of eyes with Grade 3 or Higher SLFs).

To overcome the complexity of the mixture likelihood, a latent variable Z_i , i = 1, 2 is introduced in the model to indicate in which component of the correlated binary model the observation y_i , i = 1, 2 belongs to, that is,

 $Z_i = \begin{cases} 1 & \text{if the observation belong to } MBern(p) \\ 0 & \text{if the observation belong to } Bin(2,p) \end{cases}$

The joint distribution of the augmented data (Y_i, Z_i) , i = 1, 2, is given by

$$\begin{split} P(Y = y_i, Z = z_i | \, p, \rho) \\ &= \rho^{z_i} \, p^{\frac{y_i z_i}{2}} \, (1-p)^{(2-y_i)\frac{z_i}{2}} \, (1-\rho)^{1-z_i} \, \begin{pmatrix} 2 \\ y_i \end{pmatrix} \, p^{y_i \, (1-z_i)} \, (1-p)^{(2-y_i)(1-z_i)} \end{split}$$

The probability p links to the regression variables through a logit transformation as follow: $logit(p) = \beta_o + \beta_1 lens$

It is assumed that β_o , β_1 and ρ to be independent with a non-informative prior N(0, 1000) for β_o and β_1 , and beta(0.5, 0.5) for ρ . The Metropolis sampler algorithm as implemented in the SAS/STAT MCMC procedure¹¹ will be used to estimate the posterior distributions of the parameters (β_o , β_1 , ρ). Inferences will be made based on a posterior credible interval for the relevant parameters.

Bayesian Estimation and Statistical Evaluation of Hypothesis:

The null and alternative hypotheses for Grade 3 or higher SLFs of the investigational lens compared to the threshold of 5% are as follows:

$$H_o: p_T \ge 5\%$$

 $H_1: p_T < 5\%$

where p_T is the probability of a grade 3 or higher SLF across all study visits for test lens. Based on Bayesian posterior probability distribution of the proportion p_T , superiority is interpreted as 95% probability of test being statistically lower than the threshold of 5% (i.e., $p_T < 5\%$). If the upper bound of the 95% central posterior credible interval is below 5%, it will be concluded that there is 95% probability that the investigational lens is statistically significantly lower than 5% based on observed sample.

Bayesian Estimation and Statistical Evaluation of Hypothesis:

The null and alternative hypotheses for unacceptable lens fitting of the investigational lens compared to the threshold of 20% are as follows:

$$H_o: p_T \ge 20\%$$

 $H_1: p_T < 20\%$

where p_T is the probability of an unacceptable lens fitting across all study visits for test lens. Based on Bayesian posterior probability distribution of the proportion p_T , superiority is interpreted as 95% probability of test being statistically lower than the threshold of 20% (i.e., $p_T < 20\%$). If the upper bound of the 95% central posterior credible interval is below 20%, it will be concluded that there is 95% probability that the investigational lens is statistically significantly lower than 20% based on observed sample.

In the case of zero clinically significant SLF (or unacceptable lens fitting), a Bayesian hierarchical model accounting for zero-event problem will be considered¹⁶.

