14. STATISTICAL METHODS

14.1. General Considerations

Statistical Analysis will be undertaken by the sponsor or under the authority of the sponsor. A general description of the statistical methods to be implemented in this clinical trial is outlined below. More details will be included in the stand-alone Statistical Analysis Plan (SAP). The SAP will be developed and finalized prior to database lock.

Data manipulation, statistical summaries and statistical analyses will be performed using the Statistical Analysis System (SAS) software Version 9.4 or higher (SAS Institute, Cary, NC)¹¹.

Descriptive statistics will be reported for all key variables as appropriate. Continuous data will be summarized descriptively by sample size (n), mean, standard deviation (SD), median, minimum (Min) and maximum (Max). Categorical data will be summarized descriptively by frequency count (n) and percentage (%) of subjects or eyes within each category level. Summary tables will be presented by event (Baseline, Fitting, 1-Week follow-up, 2-Week follow-up, Unscheduled and Final Evaluations) and study lens type as applicable, for the analysis set of interest. The denominator for all percentages will be the number of subjects (or eyes, as applicable) with available data in the lens group under consideration. Unscheduled visits and tele-visits will be summarized separately and will be excluded from the co-primary and secondary efficacy analyses.

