14.2. Sample Size Justification

The total sample size of 140 subjects who complete the study (Visit 3) was calculated to provide adequate power in detecting statistical superiority of the Test lens relative to prespecified thresholds for binocular distance, intermediate and near logMAR VA, CLUE vision Scores, Absolute toric rotation, rotational stability, rate of unacceptable lens fitting and rate of grade 3 or higher SLFs. All co-primary effectiveness and safety hypotheses are required to achieve statistical significance for the study objective to be satisfied, therefore no adjustment for multiple primary hypotheses is necessary. Each co-primary hypothesis will be tested using a 1-sided Type I error rate of 0.025.

Thresholds for hypotheses associated with CLUE vision, comfort and, handling scores are from a meta-analysis of 14 JJVCI clinical trials of toric and multifocal toric contact lenses used by habitual contact lens wearers aged 40 to 70 years¹². In this analysis, baseline CLUE scores (for subjects' habitual contact lenses) from 14 clinical studies were analyzed to establish thresholds reflecting the "real-world" performance of contact lenses wearers in this population

JJVC CONFIDENTIAL

with respect to CLUE vision, comfort, and handling scores. Thresholds for all other endpoints were based on clinically relevant margins.

Additionally, this study was also powered to test superiority for secondary endpoints with respect to CLUE vision, comfort and, handling scores and lens fit success using a 1-sided Type I error rate of 0.025. Secondary endpoints will be tested using a fixed sequence approach. Further details on the preservation of the study overall Type I error rate are in Section 14.4.

The sample size of 140 to complete yields at least 81% overall power to detect statistical superiority for all co-primary endpoints. This sample size provides a statistical power of at least 99% for each co-primary and secondary endpoint. To account for subject drop-out approximately 155 subjects will be enrolled to ensure at least 140 subjects complete the study.

Endpoint Domain	Endpoint	Statistical Test Type (Statistically Significantly)	Sample Size	Power (%)
Primary Efficacy	Distance (4m) Binocular Visual Acuity (logMAR)	Superiority: mean VA< 0.00	9	99.1
	Intermediate (64cm) Binocular Visual Acuity (logMAR)	Superiority: mean VA< 0.17	6	99.5
	Near (40cm) Binocular Visual Acuity (logMAR)	Superiority: mean VA< 0.17	29	99.1

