Grade 3 or Higher SLFs related to study lens wear was converted to a binary response as Y=1, if a subject eye has a clinically significant SLF, and Y=0 otherwise, for analysis purposes. Historical data show *none or an extremely low rate* (<1%) for clinically significant SLFs (Grade 3 or higher) for the test lens. Assuming a correlation of 0.70 between left and right eyes, a total of 5000 replicating trials were simulated with a reference rate of 1% (worse-case scenario). Given the rare event binary outcome of slit lamp findings, each replicated sample was analyzed using a Bayesian beta-binomial model with correlated binary data (Diniz et al; 2010)¹⁴. A non-informative prior distribution, beta (0.5, 0.5) was used to model P_T (proportion of eyes with Grade 3 or higher SLF for the Test lens). For each simulated trial, the 95% central posterior credible interval constructed for the percentage of eyes with grade 3 or higher SLFs for the Test lens was calculated. The null and alternative hypothesis for statistical significance

were $P_T \ge 5\%$ and $P_T < 5\%$, respectively. With the proposed sample size, at least 99% of the estimated 95% credible intervals had the upper bound below 5%.

As indicated in Table 6, co-primary safety endpoints were powered to at least $\sim 89\%$ individually, yielding a combined power of $\sim 88\%$. With respect to co-primary efficacy, each hypothesis, was powered to $\sim 99\%$, which provided a combined power of $\sim 92\%$. Therefore, the overall combined study power for co-primary safety and co-primary efficacy hypotheses is $\sim 81\%$.

Secondary Efficacy Endpoint Sample Size Calculations:

CLUE Vision, Comfort and, Handling (Hyperopes and Myopes)

Sample size calculations for the secondary endpoints of CLUE vision, comfort, and handling scores were carried out separately for each sphere stratum (hyperopes and Myopes) for all three CLUE domains using one-sided, one-sample mean t-test, with a one-sided Type I error rate of 0.025 for each hypothesis using the *One-Sample T-Tests for Superiority by a Margin* procedure in Power Analysis & Sample Size (PASS2021) software Version 21.0.6 (NCSS LLC, Kaysville UT)¹³. The assumptions for averages and standard deviations were made based on historical values from previous studies (Table 7).

Lens Fit Success

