14.3. Analysis Populations

Safety Population:

All subjects who were administered any test article.

Per-Protocol Population:

All subjects who have successfully completed all visits and did not substantially deviate from the protocol as determined by the trial cohort review committee prior to database hard lock (Per-Protocol Population). Justification of excluding subjects with protocol deviations will be documented in a memo to file.

Intention-to-Treat (ITT) Population:

Intention-to-treat population will include all assigned subjects.

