14.4. Level of Statistical Significance

The Type I error rate of the trial will be controlled at 1-sided 0.025 level. Each co-primary safety and efficacy hypothesis will be tested using a 1-sided Type I error of 0.025. All co-primary hypotheses must be met to satisfy the study objectives and to test any secondary hypotheses.

Based on a gate keeping approach between the primary and secondary families of hypotheses, all primary endpoints must show statistical significance at one-sided 0.025 level in order to pass the full alpha level to test the secondary endpoints hypotheses.

A fixed sequence testing procedure will be utilized to test the secondary hypotheses to control the Type I error rate also in the secondary family of hypotheses. Each secondary hypotheses will be tested using a 1-sided 0.025 level following the order prespecified in section 2.3.3. Based on the fixed sequence principle, each secondary endpoint must be found statistically significant at a one-sided 0.025 level in order to proceed to the next step. If not, the testing procedure of the secondary endpoints will stop.

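### Grade 3+ slit lamp findings: the planned prior is not the one that was powered, and at the plan's own inter-eye correlation of 0.70 the pass rule has a type I error of about 4.6%, not 2.5%

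*Combined protocol and SAP*

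**What the plan says.** Section 14.2 (Sample Size Justification) describes the power simulation for Grade 3 or higher slit lamp findings (SLF): "Assuming a correlation of 0.70 between left and right eyes, a total of 5000 replicating trials were simulated with a reference rate of 1" per cent. On the prior it says: "A non-informative prior distribution, beta (0.5, 0.5) was used to model" P_T, the proportion of eyes with such a finding. Table 6 gives 89.3% power at 140 subjects.

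Section 14.5.2 (Co-Primary Safety Analyses) specifies the analysis. It has the same correlated-binary likelihood, but with logit(p) = β0 + β1·lens, the parameters being assumed "to be independent with a non-informative prior N(0, 1000) for" β0 and β1. In that section beta(0.5, 0.5) is the prior for the correlation ρ only. The decision rule is: "If the upper bound of the 95% central posterior credible interval is below 5" per cent, the lens is declared superior to the threshold.

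Section 14.4 says: "Each co-primary safety and efficacy hypothesis will be tested using a 1-sided Type I error of 0.025". The analysis set is the safety population of section 14.3 ("All subjects who were administered any test article"), so its size is not fixed at 140.

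**The concern.** A very diffuse normal prior on the logit is not neutral for a rate near zero. On the probability scale it behaves like Beta(0, 0). It puts more mass near zero than beta(0.5, 0.5) does and so pulls the upper credible bound down. Two consequences follow. The power in Table 6 does not describe the planned analysis. The planned rule is also easier to pass than the powered one, including for a lens whose true rate sits at the 5% limit.

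The plan claims a frequentist error rate of 0.025 for this hypothesis but reports no type I error for the Bayesian rule. SLF is the ocular-health co-primary and has the lowest power in Table 6. Because every co-primary must succeed, this one verdict can decide the study.

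**Working it through.** **Inputs.** n = 140 subjects with two eyes each, true rate 1% and ρ = 0.70 (section 14.2); threshold 5% and the upper bound of the 95% central credible interval (section 14.5.2); beta(0.5, 0.5) prior on ρ (section 14.5.2). I also took n from 140 to 155, because section 14.3 uses all treated subjects and about 155 are to be enrolled.

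**Likelihood (the plan's mixture).** The probabilities that a subject has 0, 1 or 2 affected eyes are

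- P0 = (1−ρ)(1−p)² + ρ(1−p)
- P1 = (1−ρ)·2p(1−p)
- P2 = (1−ρ)p² + ρp

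At ρ = 0.70:

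| p | P0 | P1 | P2 |
|---|---|---|---|
| 1% | 0.98703 | 0.00594 | 0.00703 |
| 5% | 0.93575 | 0.02850 | 0.03575 |

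For each pair of counts (one-eye subjects, two-eye subjects) the posterior of p was integrated numerically over p and ρ. The trial passes if the posterior probability of p < 5% is at least 0.975. Exact multinomial probabilities were then summed over the passing pairs.

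**Step 1: reproduce Table 6 (n = 140, p = 1%).** Beta(0.5, 0.5) on p gives 88.6% (89.0% if ρ is fixed at 0.70). The N(0, 1000) logit prior gives 93.9%. Table 6 says 89.3%, so the powered analysis was the beta one.

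**Step 2: what each rule accepts at n = 140.** Largest number of one-eye subjects that still passes:

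| Two-eye subjects | 0 | 1 | 2 | 3 |
|---|---|---|---|---|
| Planned (logit prior) | 7 | 4 | 2 | 0 |
| Powered (beta prior) | 6 | 4 | 1 | none |

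For example, three subjects with bilateral findings and no others (6 of 280 eyes, 2.1%) give an upper bound of 4.8% under the planned prior, a pass, and 5.3% under the powered prior, a fail.

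**Step 3: type I error at p = 5%, ρ = 0.70, n = 140.** Planned 4.55%; beta 3.14%. A simulation of 200,000 trials gave 4.55% and 3.12%. The difference is the probability of the three patterns (one-eye/two-eye) on which the rules disagree:

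- 7/0: C(140,7)·P1⁷·P0¹³³ = 0.04%
- 2/2: [140!/(136!·2!·2!)]·P1²·P2²·P0¹³⁶ = 1.14%
- 0/3: C(140,3)·P2³·P0¹³⁷ = 0.23%

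These sum to 1.41 points, and 3.14 + 1.41 = 4.55.

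**Step 4: sensitivity.**

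| Type I error at p = 5% | Planned | Beta |
|---|---|---|
| n = 155, ρ = 0.70 | 4.4% | 2.8% |
| n = 140–155, ρ = 0.70 | 4.0–5.2% | 2.7–3.5% |
| n = 140, ρ = 0 | 2.7% | 1.3% |
| n = 140, ρ = 0.3 | 3.4% | 2.4% |
| n = 140, ρ = 0.9 | 5.8% | 3.2% |

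At ρ = 0.9 the beta rule reaches 4.0% at n = 150. Doubling the logit prior variance to 2000, which is what the redundant constant lens term amounts to, or reading 1000 as a standard deviation, leaves 4.55%. A uniform prior on ρ gives 4.51%.

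**Step 5: zero-event fallback.** Section 14.5.2 says another model will be considered if no events occur. At p = 5%, P(no events) = 0.93575¹⁴⁰ = 0.009%, so it cannot change the error rate. At p = 1% it is 0.98703¹⁴⁰ = 16.1%; the powers above count those trials as passes.

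**Step 6: the other Bayesian tests.** For the 20% lens-fit test, and by symmetry the 80% toric tests, the gap is small: 3.2% planned against 2.6% beta (n = 140, ρ = 0.70).

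**The case against.** The strongest reply has four parts.

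- **The 4.6% is conditional.** It needs correlated eyes; at ρ = 0 the planned rule gives 1.5–2.9% over n = 140–155. This stands as a limit on the claim, but 0.70 is the plan's own assumption.
- **The prior is not the whole excess.** At n = 140 the planned rule is 4.55 − 2.50 = 2.05 points over. The prior accounts for 1.41 and the credible-interval rule with correlated eyes for the other 0.64. This also stands, so restoring the beta prior is not enough on its own. Keeping the logit prior, correcting 14.2 and calibrating the cut-off would also be coherent.
- **The practical reach is narrow.** The two rules disagree on three outcome patterns at n = 140, historical SLF was 0.0%, and the mismatch raises power. True, but a safety test is judged on how it treats a lens at the limit, and those patterns reverse the verdict. Requiring all co-primaries limits the study-wide error; it does not make the stated per-hypothesis rate correct.
- **The details may be settled elsewhere.** Section 14.1 says: "More details will be included in the stand-alone Statistical Analysis Plan (SAP"). The text supplied has no separate section that settles the prior, so this shows where a correction can go, not that it has been made.

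Section 14.2 also says that at least 99% of intervals for this endpoint fell below 5%, which contradicts Table 6. No variant tried at n = 140 and ρ = 0.70 reaches 99%, so that sentence does not rescue the planned prior.

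**Conclusion.** The concern holds. Sections 14.2 and 14.5.2 specify different priors for the same endpoint, and the power in Table 6 belongs to the one that will not be used. Under the planned prior and the plan's own correlation, the SLF test has a type I error of 4.6% at n = 140 (4.0–5.2% for n = 140–155), almost twice the stated 2.5%. The powered prior also exceeds 2.5%, by less. The result rests on the plan's mixture model and on ρ near 0.70. It concerns this one safety hypothesis, not the study-wide error, and does not mean the trial is underpowered. It should be corrected before database lock.

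**What to change.** 1. In section 14.5 place beta(0.5, 0.5) directly on p, as in 14.2, and keep beta(0.5, 0.5) on ρ. Drop the constant lens term as a tidy-up. Carry the same text into the stand-alone SAP.
2. For SLF, do one of the following: replace the unqualified 0.025 with the simulated type I error at p = 5% over a range of ρ and of safety-population size; or set the posterior cut-off from that simulation before database lock.
3. While editing 14.2, reconcile its 99% statement for SLF with the 89.3% in Table 6.

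Guide values with the beta prior, n = 140–155:

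| Cut-off | Type I error, ρ = 0.70 | Highest at ρ = 0.9 | Power at p = 1%, ρ = 0.70 |
|---|---|---|---|
| 0.98 | 2.2–2.9% | 3.35% | 87–92% |
| 0.985 | 1.7–2.2% | 2.8% | 81–88% |

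These are a guide only; no cut-off should be adopted without the sponsor's own simulation.

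**Cost.** Wording and a rerun of an existing simulation; sample size, visits and data collection do not change. Power at n = 140 returns to about the published level (88.6% rather than 93.9%). A stricter cut-off then costs about 0.3 points (0.98) or 7 points (0.985).

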14.6. Secondary Analyses

CLUE Vision, Comfort and, Handling

Secondary endpoints for CLUE vision, comfort and handling, scores after 2-weeks of lens wear will be analyzed separately using the same model as described above for primary analysis of CLUE vision scores.

The null and alternative hypothesis to test for superiority of the hyperopic subjects relative to the pre-defined threshold of 46 for the investigational lens is as follows:

 $H_o: \mu_{Hyperopes} \le 46$ $H_A: \mu_{Hyperopes} > 46$

Where $\mu_{Hyperopes}$ represents the population mean for the investigational lens after 2-weeks lens wear with respect to CLUE handling scores for hyperopic subjects. The Test lens will be declared statistically significantly greater than 46 if the one-sided p-values is below 0.025.

The null and alternative hypothesis to test for superiority of the hyperopic subjects relative to the pre-defined threshold of 38 for the investigational lens is as follows:

 $H_o: \mu_{Hyperopes} \le 38$ $H_A: \mu_{Hyperopes} > 38$

Where $\mu_{Hyperopes}$ represents the population mean for the investigational lens after 2-weeks lens wear with respect to CLUE comfort scores for hyperopic subjects. The Test lens will be declared statistically significantly greater than 38 if the one-sided p-values is below 0.025.

The null and alternative hypothesis to test for superiority of the myopic subjects relative to the pre-defined threshold of 55 for the investigational lens is as follows:

$$\begin{array}{l} H_o: \mu_{Myopes} \leq 55 \\ H_A: \mu_{Myopes} > 55 \end{array} \end{array}$$

Where μ_{Myopes} represents the population mean for the investigational lens after 2-weeks lens wear with respect to CLUE handling scores for myopic subjects. The investigational lens will be declared statistically significantly greater than 55 if the one-sided p-values is below 0.025.

The null and alternative hypothesis to test for superiority of the hyperopic subjects relative to the pre-defined threshold of 41 for the Test lens is as follows:

$$H_o: \mu_{Hyperopes} \le 41$$

 $H_A: \mu_{Hyperopes} > 41$

Where $\mu_{Hyperopes}$ represents the population mean for the investigational lens after 2-weeks lens wear with respect to CLUE vision scores for hyperopic subjects. The investigational lens will be declared statistically significantly greater than 41 if the one-sided p-values is below 0.025.

The null and alternative hypothesis to test for superiority of the myopic subjects relative to the pre-defined threshold of 51 for the investigational lens is as follows:

$$\begin{array}{l} H_o: \mu_{Myopes} \leq 51 \\ H_A: \mu_{Myopes} > 51 \end{array}$$

Where μ_{Myopes} represents the population mean for the investigational lens after 2-weeks lens wear with respect to CLUE comfort scores for myopic subjects. The investigational lens will be declared statistically significantly greater than 51 if the one-sided p-values is below 0.025.

The null and alternative hypothesis to test for superiority of the myopic subjects relative to the pre-defined threshold of 46 for the investigational lens is as follows:

 $\begin{array}{l} H_o: \mu_{Myopes} \leq 46 \\ H_A: \mu_{Myopes} > 46 \end{array}$

Where μ_{Myopes} represents the population mean for the investigational lens after 2-weeks lens wear with respect to CLUE vision scores for myopic subjects. The Test lens will be declared statistically significantly greater than 46 if the one-sided p-values is below 0.025.

Lens Fit Success (Number of lenses required to achieve lens optimization)

Number of lenses required to achieve lens optimization will be analyzed using a Bayesian betabinomial model with correlated binary data¹⁴.

Bayesian Estimation and Statistical Evaluation of Hypothesis:

Superiority of the Test lens relative to the pre-defined threshold with respect to unacceptable lens fitting will be evaluated using Bayesian statistics. The null and alternative hypotheses for evaluating superiority of the investigational lens relative to 90% are as follows:

$$H_0: p_T \le 90\%$$

 $H_A: p_T > 90\%$,

where p_T is the probability of event (i.e., proportion of subjects to achieve optimization in 4 lenses or less while wearing the test lens). Based on Bayesian posterior probability distribution of the proportion p_T , superiority is interpreted as 95% probability of the Test lens being statistically greater than the pre-defined threshold of 90% (i.e., $p_T > 0.90$) with respect to unacceptable lens fitting rate. If the upper bound of the 95% central posterior credible interval is above 0.90, it can be concluded that there is 95% probability that the investigational lens is superior to the 90% threshold (statistically better) based on the observed sample.

In the event that all subjects' vision was optimized in 4 lenses (2 pairs) or less (i.e., zero optimization events), a Bayesian hierarchical model accounting for zero event problem will be considered¹⁶.

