2.3.3. Secondary Efficacy Hypotheses

A fixed sequence approach will be used to control the type I error. The order of testing secondary hypotheses are as follows:

- 1. After approximately 2-Weeks of wear, the mean CLUE *handling* score of the Test lens will be statistically significantly better (greater) than 46 for the hyperope population.
- 2. After approximately 2-Weeks of wear, the mean CLUE *comfort* score of the Test lens will be statistically significantly better (greater) than 38 for the hyperope population.
- 3. After approximately 2-Weeks of wear, the mean CLUE *handling* score of the Test lens will be statistically significantly better (greater) than 55 for the myope population.
- 4. After approximately 2-Weeks of wear, the mean CLUE overall *quality of vision* score of the Test lens will be statistically significantly better (greater) than 41 for the hyperope population.
- 5. After approximately 2-Weeks of wear, the mean CLUE *comfort* score of the Test lens will be statistically significantly better (greater) than 51 for the myope population.
- 6. After approximately 2-Weeks of wear, the mean CLUE overall *quality of vision* score of the Test lens will be statistically significantly better (greater) than 46 for the myope population.
- 7. The percentage of subjects who are fit with the optimized lens pair in 4 lenses or less will be statistically significantly better (greater) than 90%.

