The reference rate for lens fit success was based on the worst-case scenario of 99%, given the historical results show 100% (Table 6). Lens fit is a binary response and is defined as follows:

Lens Fit Success :
$$Y = \begin{cases} 1 & \text{if a subjects' vision is optimized in 2 pairs or less} \\ 0 & \text{Otherwise} \end{cases}$$

Historical data of the Test lens indicates there is an extremely high rate (100%) for lens fit success. Assuming a correlation of 0.70 between left and right eyes, a total of 5000 replicating trials were simulated with reference rate of 99% for the percentage of eyes optimized in 4 lenses (2 pairs) or less. Given the high event rate of the binary outcome, Y=1, each replicated sample was analyzed using a Bayesian beta-binomial model with correlated binary data (Diniz et al; 2010)¹⁴. A non-informative prior distribution, beta(1, 1) was used to model P_T (proportion of eyes with optimized in 4 lenses or less). For each simulated trial, the 95% central posterior credible interval (CrI) constructed for the percentage of eyes optimized in 4 lenses or less was calculated. The null and alternative hypothesis for determining statistical significance were $P_T \leq 90\%$ and $P_T > 90\%$, respectively. With the proposed sample size, the percentage of eyes optimized in 4 lenses or less has at least 99% power, i.e., 99% of the estimated 95% CrIs had the lower bound above 90%.

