where p_T is the percentage of eyes with absolute toric rotation $\leq 10^\circ$ (or lens stability $\leq 5^\circ$) for the investigational lens. Based on Bayesian posterior probability distribution of the proportion p_T , superiority is interpreted as 95% probability of the investigational lens being statistically higher than the threshold of 80% (i.e., $p_T > 80\%$). If the lower bound of the 95% central posterior credible interval is above 80%, it will be concluded that there is 95% probability that the investigational lens is statistically significantly higher than 80% based on observed sample.

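### Lens fit success: Section 14.6 declares superiority over 90% from the upper credible bound; a lens at exactly 90% would then pass about 96% of the time

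*Combined protocol and SAP*

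**What the plan says.** Lens fit success is the seventh and last hypothesis in the fixed sequence of Section 2.3.3: "The percentage of subjects who are fit with the optimized lens pair in 4 lenses or less" is to be shown greater than 90%.

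Section 14.6 gives the hypotheses for "evaluating superiority of the investigational lens relative to 90% are as follows": H0: p_T ≤ 90%, HA: p_T > 90%. It explains superiority as a 95% probability that p_T exceeds 0.90. The decision rule then reads "If the upper bound of the 95% central posterior credible interval is above 0.90", in which case superiority is concluded. The same paragraph describes the comparison as being "with respect to unacceptable lens fitting rate", which is a different endpoint.

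Three other places bear on the rule:

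- Section 14.2, power for this same endpoint: "99% of the estimated 95% CrIs had the lower bound above 90" (percent).
- Section 14.5.1, the parallel tests of toric rotation and stability against 80%: "If the lower bound of the 95% central posterior credible interval is above 80" (percent).
- Section 14.4: "Each secondary hypotheses will be tested using a 1-sided 0.025 level following the order prespecified in section 2.3.3".

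**The concern.** For a hypothesis that a rate exceeds a limit, the evidence lies in the lower end of the interval. If only the upper end has to clear 90%, the rule asks whether the data are compatible with a rate above 90%, not whether they demonstrate one. An observed rate below 90% can then be reported as superior to 90%.

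The rule also fails the meaning that Section 14.6 gives to superiority, because it can be met when the posterior probability that p_T > 0.90 is very small. At stake is the lens fit success claim and the statement in Section 14.4 that Type I error is controlled within the secondary family.

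**Working it through.** **Inputs.** n = 140 completers, reference rate 99%, prior beta(1,1), 95% central interval and limit 90% (all Section 14.2); nominal 1-sided level 0.025 (Section 14.4); stated power 99.8% (Table 6). The check treats the subject as the unit, as Sections 2.2.3, 2.3.3 and 14.6 do.

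**Method.** With x successes in n, the posterior is beta(1 + x, 1 + n − x). Its 2.5% and 97.5% quantiles are the interval bounds. Each rule becomes a cut-off: the smallest x at which the relevant bound exceeds 0.90. The chance of passing at a true rate p is then the exact binomial tail P(X ≥ cut-off | n, p).

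**Step 1: the plan's own figure.** The lower bound first exceeds 0.90 at x = 133 (bound 0.9004; at x = 132 it is 0.8913). At p = 0.99, P(X ≥ 133) = 99.99%, close to the stated 99.8%, which came from a simulation of correlated eyes. Agreement in power does not by itself identify the rule, since the upper-bound rule also passes almost surely at 99%. It is the wording of Section 14.2 that ties the stated power to the lower bound.

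**Step 2: the rule as written.** The upper bound first exceeds 0.90 at x = 120 (bound 0.9054; at x = 119 it is 0.8996). So 120/140 = 85.7% is declared superior to 90%. At that result the posterior is beta(121, 21) and P(p_T > 0.90) = 0.042, against the 95% that Section 14.6 says superiority means.

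**Step 3: chance of declaring success, n = 140.**

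| True rate | Written rule (≥ 120) | Lower-bound rule (≥ 133) |
|---|---|---|
| 80% | 5.2% | < 0.01% |
| 82% | 15.0% | < 0.01% |
| 85% | 46.4% | 0.02% |
| 86% | 59.8% | 0.05% |
| 88% | 83.3% | 0.41% |
| 90% | 96.1% | 2.57% |
| 99% | > 99.99% | 99.99% |

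**Step 4: sensitivity at a true rate of 90%, written rule.**

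- All 155 enrolled subjects: cut-off 133/155, pass probability 96.4%.
- Prior beta(0.5, 0.5), n = 140: cut-off 119/140, 97.8%.
- Correlated-eyes model, inter-eye correlation 0.70, 5,000 simulated trials: 97.0% with a flat prior on p, 97.3% with the N(0, 1000) prior on the logit. The lower-bound rule gives 1.6% and 3.7% in the same two settings.
- Correlated-binary model with the Section 14.5.1 priors, giving both eyes the subject's result (an assumption): cut-off 119/140, 97.8%. The lower-bound cut-off is 132/140, with 5.3% at the limit.

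Under the written rule, every variant gives 96% to 98% where 2.5% is intended.

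**The case against.** The best case for leaving this alone is that the intent is plain and the consequence small. The hypotheses, the stated meaning of superiority, the power calculation and the alpha level all point to the lower bound, so an analyst would probably notice the slip. The test comes after nine co-primary and six earlier secondary hypotheses have all succeeded, and it passes no alpha onward. The 96% is therefore conditional on reaching the test with a true rate of exactly 90%. The historical rate is 100% and the planning rate 99%. The two rules disagree only for 120 to 132 successes, which has probability about 0.01% at 99%, 0.7% at 98% and 6% at 97%. At 95% it is about 40%, but a pass there is not a false claim. Section 14.1 also promises a stand-alone SAP, which might put the wording right.

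Most of this stands and limits the reach of the error. It is also fair to say that the toric tests in Section 14.5.1 are a parallel rule for other endpoints rather than a direct contradiction; the direct conflicts are with Sections 14.2 and 14.4 and within Section 14.6 itself.

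None of it makes the rule correct. Section 14.6 is the only analysis section that states the criterion for this endpoint, and Section 14.10 says the analysis will follow the sections above it. Reversing the bound after results are known would change a prespecified success criterion. Section 14.2 also notes that this is the first dispensing study since the lens design changed, so the 99% assumption should not be what protects the claim.

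**Conclusion.** The concern holds. As written, the rule does not test H0: p_T ≤ 90% at a 1-sided 0.025 level. If the test is reached, a lens at exactly 90% passes about 96% of the time and one at 85% about 46%; a clearly poor lens at 80% passes only about 5%. The practical weakness therefore lies between roughly 85% and 90%.

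These figures rest on a subject-level model with 140 subjects and a beta(1,1) prior. Changing the sample size, the prior or the handling of eyes moves the figure at 90% only between 96% and 98%. The primary conclusions and the first six secondary tests are unaffected. The correction is still required, because the decision threshold is wrong as stated and is easily put right before database lock.

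**What to change.** In the lens fit success paragraph of Section 14.6, require the lower bound of the 95% central credible interval to be above 0.90, and replace the two references to unacceptable fitting with lens fit success.

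State the prior in the same paragraph, since Section 14.6 gives none and the cut-off depends on it. With the beta(1,1) prior on the success rate from Section 14.2, the cut-off is 133/140 and the error at the limit 2.6%, marginally above 2.5%. With the logit-scale priors of Section 14.5.1, and both eyes given the subject's result, it would be 132/140 and 5.3%. The model in Section 14.5.1 puts normal priors on logit coefficients, so using beta(1,1) means writing the model in terms of p directly; the text should say so.

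A separate point, not needed for this correction: the endpoint is defined per subject in Sections 2.2.3, 2.3.3 and 14.6, whereas Section 14.2 states that "the percentage of eyes optimized in 4 lenses or less has at least 99% power". The unit of analysis should be reconciled.

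The cost is a wording change in one paragraph, carried into the stand-alone SAP. No data or subjects are added, and in the subject-level check power at the planned 99% rate stays above 99.9%.
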